The key toxicological findings attributed to LY3022855 administration in preclinical studies included reversible mild-to-moderate increases in serum transaminases (AST and alanine aminotransferase [ALT]) and target organ effects in liver (Kupffer cell hypertrophy/hyperplasia). No histological changes in the liver were noted to correlate with the transaminase increases, nor were any changes noted in liver functional parameters (that is, alkaline phosphatase, bilirubin, or coagulation). Therefore, based on the small magnitude of the elevations and their limited impact to the overall health of the animal, the increases in ALT and AST were not considered adverse. The effect on Kupffer cells, specialized macrophages in the liver that play an important role in the clearance of several serum enzymes, including AST and CK, was regarded as immunomodulatory and was possibly associated with elevations in circulating CSF-1 levels.

In clinical studies of LY3022855 monotherapy, increases in serum AST and CK levels (mostly Grades 1 and 2) were noted in 19 and 17 patients, respectively, who received LY3022855 (of the total 64 patients) as of 28 January 2017. The majority of these patients experienced elevations in both enzymes and received 1.25 mg/kg Q2W, 2.5 mg/kg QW, 100 mg QW, or 150 mg QW of LY3022855. One case of a dose-limiting adverse event (AE) of Grade 4 rhabdomyolysis leading to Grade 4 acute renal failure was reported in a patient treated with LY3022855 1.25 mg/kg QW. The patient recovered from the events following discontinuation of study treatment. One of the 3 patients administered the dose of 150 mg QW experienced a Grade 3 CK elevation with associated elevated levels of serum and urine myoglobin. Although no similar observations were noted in additional 3 patients, the dose of 100 mg QW was selected as the recommended Phase 2

dose for LY3022855 due to potential safety issues related to the QW dosing of 150 mg as evidenced by the laboratory abnormalities induced by LY3022855. None of the patients with increased levels of AST experienced clinical symptoms suggestive of hepatic toxicity, nor were elevations of bilirubin noted at the time of the AST elevations. Among all patients with AST and CK elevations, only 1 patient who received the dose of 2.5 mg/kg QW of LY3022855 was discontinued from the study due to drug-related increases in CK (Grade 3), AST (Grade 3), and lactate dehydrogenase (LDH; Grade 1).

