Comparatively, preclinical and clinical studies on CSF-1R–targeted monoclonal antibodies have shown asymptomatic increases in short-lived enzymes, such as LDH, CK, and AST (Cassier et al. 2015; Zhou et al. 2015). These increases in the levels of serum enzymes can be the result of decreases in Kupffer cells, depletion of which is consistent with the expected pharmacologic effect of CSF-1R pathway inhibition on Kupffer cells (Radi et al. 2011).

In clinical studies of LY3022855 monotherapy, increases in serum amylase and lipase (mostly Grades 1 and 2) were noted in 4 and 9 patients, respectively, who received single-agent LY3022855 (of the total of 64 patients) as of 28 January 2017. These patients were treated with 1.25 mg/kg QW, 1.25 mg/kg Q2W, 100 mg QW, or 150 mg QW of LY3022855. One of these patients who was treated with LY3022855 1.25 mg/kg QW developed mild-to-moderate increases in amylase and lipase levels and was ultimately diagnosed with Grade 3 pancreatitis, determined to be dose-limiting. The patient recovered from pancreatitis following study treatment interruption but was subsequently removed from study due to the event. There were no other cases of pancreatitis reported with administration of a single-agent LY3022855 as of 28 January 2017.

These data suggest that elevations of serum levels of enzymes AST, CK, amylase, and lipase, are not necessarily indicative of end organ damage, thus, supporting modification of the DLT criteria in this protocol to allow flexibility to continue dosing with Grade ≥ 2 elevations of AST, CK, amylase, and lipase in certain situations as described in Section 7.2.2.1.

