	
Grade 2 (AST or ALT $> 3.0 \times$ULN and $\leq 5.0 \times$ULN and/or TB $> 1.5 \times$ULN and $\leq 3.0 \times$ULN)
	
 Hold study drug/study regimen dose until Grade 2 resolution to Grade ≤ 1. If toxicity worsens, then treat as Grade 3 or Grade 4. If toxicity improves to Grade ≤ 1 or baseline, resume study drug/study regimen after completion of steroid taper. 	
For Grade 2:
 
 Regular and frequent checking of LFTs (eg, every 1 to 2 days) until elevations of these are improving or resolved. If no resolution to Grade ≤ 1 in 1 to 2 days, consider, as necessary, discussing with study physician. If event is persistent (> 3 to 5 days) or worsens, promptly start prednisone 1 to 2 mg/kg/day PO or IV equivalent. If still no improvement within 3 to 5 days despite 1 to 2 mg/kg/day of prednisone PO or IV equivalent, consider additional workup and start prompt treatment with IV methylprednisolone 2 to 4 mg/kg/day. If still no improvement within 3 to 5 days despite 2 to

		
For asymptomatic Grade 2 AST (only if accompanied by Grade ≤ 1 ALT and Grade ≤ 1 TB and no change of ALT or TB from baseline levels):
 
 Continue dosing with both LY3022855 and durvalumab or tremelimumab 	
4 mg/kg/day of IV methylprednisolone, promptly start immunosuppressives (ie, mycophenolate mofetil).^a Discuss with study physician if mycophenolate mofetil is not available. Infliximab should NOT be used.
 
 Once the patient is improving, gradually taper steroids over ≥ 28 days and consider prophylactic antibiotics, antifungals, and anti-PJP treatment (refer to current NCCN guidelines for treatment of cancer-related infections [Category 2B recommendation]).^a

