	
Grade 3 or 4 (Grade 3: AST or ALT $>5.0 \times$ULN and $\leq 20.0 \times$ULN and/or TB $>3.0 \times$ULN and $\leq 10.0 \times$ULN) (Grade 4: AST or ALT $>20 \times$ULN and/or TB $>10 \times$ULN)
	
For Grade 3: For elevations in transaminases $\leq 8 \times$ ULN, or elevations in bilirubin $\leq 5 \times$ ULN:
 
 Hold study drug/study regimen dose until resolution to Grade ≤ 1 or baseline Resume study drug/study regimen if elevations downgrade to Grade ≤ 1 or baseline within 14 days and after completion of steroid taper. Permanently discontinue study drug/study regimen if the elevations do not downgrade to Grade ≤ 1 or baseline within 14 days 
For asymptomatic Grade 3 AST up to $\leq 8 \times$ ULN (only if accompanied by Grade ≤ 1 ALT and Grade ≤ 1 TB and no change of ALT or TB from baseline levels):
	
For Grade 3 or 4:
 
 Promptly initiate empiric IV methylprednisolone at 1 to 4 mg/kg/day or equivalent. If still no improvement within 3 to 5 days despite 1 to 4 mg/kg/day methylprednisolone IV or equivalent, promptly start treatment with immunosuppressive therapy (ie, mycophenolate mofetil). Discuss with study physician if mycophenolate is not available. Infliximab should NOT be used. Perform hepatology consult, abdominal workup, and imaging as appropriate. Once the patient is improving, gradually taper steroids over ≥ 28 days and consider prophylactic antibiotics, antifungals, and anti-PJP treatment (refer to current NCCN guidelines for treatment of cancer-related infections [Category 2B recommendation]).^a

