		
baseline levels)
 
 • Hold LY3022855, and continue dosing with durvalumab or tremelimumab. • If AST downgrades to Grade ≤ 2, after holding LY3022855, resume dosing with LY3022855 and durvalumab or tremelimumab. • If Grade 3 AST recurs after resumption of dosing with both agents, hold LY3022855 dosing. Continue dosing durvalumab or tremelimumab. Resume treatment with the combination of LY3022855 and durvalumab or tremelimumab if AST remains asymptomatic and downgrades to Grade ≤ 2. 
For elevations in transaminases $>8 \times$ ULN or elevations in bilirubin $>5 \times$ ULN, discontinue study drug/study regimen.
 
Permanently discontinue study drug/study regimen for any case meeting Hy's law criteria (AST and/or ALT $>3 \times$ ULN + bilirubin $>2 \times$ ULN without initial findings of cholestasis (ie, elevated alkaline P04) and in the absence of any alternative cause.^b
 
For Grade 4:
 
Permanently discontinue study drug/study regimen.
	
--	--	---	--

Nephritis or renal dysfunction (elevated serum creatinine)	Any Grade	General Guidance	For Any Grade: 
 Consult with nephrologist. Monitor for signs and symptoms that may be related to changes in renal function (eg, routine urinalysis, elevated serum BUN and creatinine, decreased creatinine clearance, electrolyte imbalance, decrease in urine output, or proteinuria). Patients should be thoroughly evaluated to rule out any alternative etiology (eg, disease progression or infections). Steroids should be considered in the absence of clear alternative etiology even for low-grade events (Grade 2), in order to prevent potential progression to higher grade event.
	Grade 1 (Serum creatinine > 1 to $1.5 \times$ baseline; $>$ ULN to $1.5 \times$ ULN)	No dose modifications.	For Grade 1: 
 Monitor serum creatinine weekly and any accompanying symptoms. 
 If creatinine returns to baseline, resume its regular monitoring per study protocol. If creatinine worsens, depending on the severity, treat as Grade 2, 3, or 4. Consider symptomatic treatment, including hydration, electrolyte replacement, and diuretics.

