			
lipase, corticosteroid treatment is not indicated as long as there are no other signs or symptoms of pancreatic inflammation.
 
 If a patient experiences an AE that is thought to be possibly of autoimmune nature (eg, thyroiditis, pancreatitis, hypophysitis, or diabetes insipidus), the investigator should send a blood sample for appropriate autoimmune antibody testing.
	Grade 1	No dose modifications.	
For Grade 1 (including those with asymptomatic TSH elevation):
 
 Monitor patient with appropriate endocrine function tests. For suspected hypophysitis/hypopituitarism, consider consultation of an endocrinologist to guide assessment of early morning ACTH, cortisol, TSH and free T4; also consider gonadotropins, sex hormones, and prolactin levels, as well as cosyntropin stimulation test (though it may not be useful in diagnosing early secondary adrenal insufficiency). If TSH $< 0.5 \times$ LLN, or TSH $> 2 \times$ ULN, or consistently out of range in 2 subsequent measurements, include free T4 at subsequent cycles as clinically indicated and consider consultation of an endocrinologist.

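### For isolated asymptomatic AST elevation, the Attachment 7 dosing column continues the checkpoint inhibitor while the management column of the same rows calls for systemic steroids and states no exception

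*Protocol*

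**What the plan says.** Protocol Attachment 7 (Specific Immune-Mediated Reactions, Hepatitis) has a dose-modification column and a toxicity-management column for each grade.

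**Dosing column.** It makes an exception for asymptomatic AST elevation when ALT and total bilirubin are Grade 1 or below and have not moved from baseline. At Grade 2 the instruction is "Continue dosing with both LY3022855 and durvalumab or tremelimumab". At Grade 3, up to 8 x ULN, it is "Hold LY3022855, and continue dosing with durvalumab or tremelimumab"; LY3022855 comes back when AST falls to Grade 2 or lower, and no taper is mentioned.

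**Management column.** It makes no such exception. The Grade 2 cell says "If event is persistent (> 3 to 5 days) or worsens, promptly start prednisone 1 to 2 mg/kg/day PO or IV equivalent", then IV methylprednisolone 2 to 4 mg/kg/day and then mycophenolate if there is no response. The Grade 3 or 4 cell opens with "Promptly initiate empiric IV methylprednisolone at 1 to 4 mg/kg/day or equivalent", with mycophenolate for non-response. Both cells call for a taper of at least 28 days once the patient improves.

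**Background.** Section 5.1.2 reports that "increases in serum AST and CK levels (mostly Grades 1 and 2) were noted in 19 and 17 patients", of 64 treated with LY3022855 alone. It concludes that such enzyme rises "are not necessarily indicative of end organ damage". Section 7.2.2.1 leaves isolated asymptomatic Grade 3 AST out of the DLT definition. The SAP does not address the point.

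**The concern.** The protocol anticipates this laboratory finding and links it to CSF-1R inhibition acting on Kupffer cells. It builds a special category for it, but only in the column on study-drug dosing. The neighbouring column, on what else to do for the same patient, is written as if the category did not exist. One site could continue the checkpoint inhibitor and only monitor. Another could continue it and start systemic steroids. Both could cite the same row.

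Whether a patient on an immune-activating drug also receives immunosuppression should not turn on that reading. This is a safety matter first. It also bears on what the study reports: antitumor activity is a secondary objective, and immune-cell subsets and activation are exploratory objectives. Steroid use that varies by site would be hard to separate from treatment effects in small descriptive cohorts.

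**Working it through.** There is no design figure to reproduce. The check sets the cells side by side and then asks whether any other text settles the question.

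**1. Who falls in the category.** By the row definitions, Grade 2 is AST above 3 and up to 5 x ULN. The Grade 3 exception covers AST above 5 and up to 8 x ULN. In both, ALT and bilirubin must be Grade 1 or below and unchanged.

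**2. The same patient in each column.**

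| | Grade 2 | Grade 3, up to 8 x ULN |
|---|---|---|
| LY3022855 | continues | held |
| Durvalumab or tremelimumab | continues | continues |
| Steroids | if lasting more than 3 to 5 days or worsening: prednisone 1 to 2 mg/kg/day | at once: IV methylprednisolone 1 to 4 mg/kg/day |
| Restart under the AST exception | not needed | at AST Grade 2 or lower |
| Restart under the general hepatitis bullets | after the taper | after the taper |

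The persistence condition at Grade 2 may be met often. The exception keeps both drugs going at Grade 2, and after a Grade 3 rise it restarts LY3022855 while AST may still be Grade 2. A rise outlasting 3 to 5 days is therefore foreseeable. This is an inference, not a figure in the documents.

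**3. Is the exception stated elsewhere?** No.
- The General Considerations table repeats the default for persistent Grade 2 or any Grade 3 event, "promptly start prednisone 1 to 2 mg/kg/day PO or IV equivalent", without mentioning AST.
- Section 7.5.1 permits immunosuppressants for product-related adverse events, so it does not limit the steroid cells.
- The parallel enzyme signals do have matching text. For modest asymptomatic rises in amylase and "lipase, corticosteroid treatment is not indicated as long as there are no other signs or symptoms of pancreatic inflammation". For asymptomatic CK, the non-immune table calls for evaluation and monitoring, and sends a Grade 3 case to the immune guidelines only on evidence of possible immune-mediated organ damage.

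**4. What the restart ambiguity is worth.** A 28-day taper spans 28/7 = 4 weekly LY3022855 dates and 28/14 = 2 durvalumab dates. If the taper condition applies, at least a full cycle of weekly LY3022855 is at issue after a Grade 3 rise, whereas the exception alone allows restart as soon as AST reaches Grade 2.

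**5. How often AST rises.** 19/64 = 0.297, exact (Clopper-Pearson) 95% CI 0.189 to 0.424. This counts any grade, pools several monotherapy regimens and is described as mostly Grades 1 and 2. Grade 1 calls only for monitoring. Section 5.1.2 does not say how many rises were Grade 2 or higher with ALT and bilirubin unchanged.

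**6. The steroid amounts.** At the protocol's 75-kg reference weight:
- prednisone: 75 x 1 to 75 x 2 = 75 to 150 mg/day
- methylprednisolone: 75 x 1 to 75 x 4 = 75 to 300 mg/day

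Across the 40 to 120 kg range of the protocol's PK simulations, these become 40 to 240 mg/day and 40 to 480 mg/day.

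**The case against.** The best defence is that the steroid column does not run unfiltered. Attachment 7 introduces its steps as recommendations for immune-mediated events and asks sites to rule out other causes. The hepatitis row repeats that request. Section 7.2.4.1 has the investigator judge whether the event is immune related, and Attachment 8 defines an immune-related event as one with no clear alternative cause. Section 5.1.2 supplies an alternative cause, so a careful site could decide that the steroid cells do not apply. This stands as a route a site might take. It does not close the gap, because the AST category was placed inside the immune-mediated hepatitis rows and nothing there releases it from their steroid steps.

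The lipase and amylase comparison also cuts both ways: drafters who could write an exemption there may have left one out here on purpose. If so, the text should say so.

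Several stronger readings are tempting but unsupported:
- **Two opposite orders, or both drugs continued alongside immediate high-dose steroids.** Neither row says this. At Grade 3 LY3022855 is held. At Grade 2 steroids are conditional and start below the 2 to 4 mg/kg/day that the General Considerations call high-dose. The dosing column never forbids steroids. The defect is a missing exception.
- **About 12 of 40 Part B patients affected** (0.297 x 40 = 11.9). That applies an any-grade monotherapy rate to a narrower category, at a dose not yet set.
- **A breach of the 10 mg/day prednisone limit.** Treatment of product-related events is exempt from it.
- **Steroids here are unnecessary.** Section 5.1.2 supports changed DLT criteria and continued dosing. It does not discuss steroids.
- **The Attachment 10 change log settles it.** It shows a no-steroid line absent from the current table, but it describes superseded text and is not relied on.

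**Conclusion.** The inconsistency is real and safety-relevant. For isolated asymptomatic AST elevation, the dosing column continues the checkpoint inhibitor (with LY3022855 at Grade 2, without it at Grade 3 up to 8 x ULN). The adjacent column calls for systemic steroids, conditionally at Grade 2 and promptly at Grade 3, with no stated exception. Whether restart must wait for the taper is unresolved as well.

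The event is anticipated, but the number of patients who would meet the conflict cannot be estimated. The 29.7% any-grade rate is context, not an estimate of those affected. No figure supports a size or direction of bias in the endpoints; site-dependent steroid use is a possibility the text leaves open.

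The conclusion rests on the current Attachment 7 tables alone. It assumes that sites apply the management cell of the row in which a patient's AST grade falls.

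**What to change.** Reconcile the two columns of the Grade 2 and Grade 3 hepatitis rows for this category. The text should state whether the steroid steps apply to it, and whether resumption must wait for a completed taper. Which rule to adopt is for the sponsor's clinical team.

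The cost is about one paragraph in Attachment 7 at the next amendment. A listing flag for systemic steroids given for isolated AST is optional: Section 7.5 already requires concomitant medications to be recorded, and SAP Section 6.7 lists and summarizes them by cohort.

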7.2.4.1. Dose Delays for Adverse Events

Study treatment may be held for a maximum of 28 days; see exception for an immune-related AE below. If appropriate, and in the opinion of the investigator and upon agreement with the sponsor, study treatment may resume upon resolution of clinically significant AEs to baseline or improvement to Grade <2. If AEs, see exception for an immune-related AE, do not resolve to baseline or improve to Grade <2 within 28 days following the last administered dose, study treatment should be permanently discontinued and the patient should be discontinued from the trial. If treatment is held, the day of treatment should continue as if no drug interruption has occurred. For example, if study drug is held on D6 of a cycle and AEs have resolved by D10 (4 days later), the study drugs should be resumed per the original schedule. If the original schedule results in a study drug being held for >28 days, the study drug may not be resumed. One or both study drugs may be held, resumed, or discontinued.

If the AE is an immune related AE as outlined in [Attachment 7](#), and if the treatment management guidelines outlined in [Attachment 7](#) are followed and documented in the patient's medical record, treatment may be held for >28 days to allow taper of high dose steroids. Treatment may resume in this setting only upon resolution of immune AEs to baseline or improvement to Grade <2, and only if deemed clinically appropriate by the treating physician and agreed to by the sponsor. If steroids cannot be tapered as outlined in [Attachment 7](#), and/or AEs do not resolve to < Grade 2, the patient may not be resumed on study treatment.

For the purposes of documentation, the investigator must assess if the toxicity is considered at least possibly related to study treatment (that is, the combination regimen) and if the AE is considered to be immune related. Investigators are encouraged to consult the sponsor for additional guidance.

For AEs that are considered at least possibly related to study treatment, the following dose adjustment guidance may be applied:

- Treat each of the toxicities with maximum supportive care (including holding the study drug[s] suspected of causing the toxicity where required).
- If the symptoms promptly resolve with supportive care, consideration should be given to continuing the same dose of study drugs along with appropriate continuing supportive care.

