- All dose modifications should be documented with clear reasoning and documentation of the approach taken.

In addition, there are certain circumstances in which study drugs should be permanently discontinued (refer to [Attachment 7](#)).

Following the first dose of study drugs, subsequent administration of study drugs can be modified based on toxicities observed (refer to [Attachment 7](#)).

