8.1.5. Safety Monitoring

The Lilly CRP/CRS will monitor safety data throughout the course of the study.

Representatives from Lilly Global Patient Safety will specifically monitor SAEs. Lilly will review SAEs within time frames mandated by company standard operating procedures.

- If a study patient experiences elevated ALT $\geq 5 \times$ ULN and elevated TB $\geq 2 \times$ ULN, clinical and laboratory monitoring should be initiated by the investigator.
- For patients entering the study with ALT $\geq 3 \times$ ULN, monitoring should be triggered at ALT $\geq 2 \times$ baseline.

Details for hepatic monitoring depend upon the severity and persistence of observed laboratory test abnormalities. To ensure patient safety and comply with regulatory guidance, the investigator is to consult with the Lilly CRP/CRS regarding collection of specific recommended clinical information and follow-up laboratory tests (see [Attachment 3](#)).

Refer to [Attachment 8](#) for details about AESIs.

Refer to [Attachment 7](#) for additional details on Toxicology management guidelines.

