
may be permanently discontinued. Please refer to guidelines below.
 
Grade 4 Permanently discontinue study drug/study regimen.
 
Note: For Grade ≥ 3 asymptomatic amylase or lipase levels, hold study drug/study regimen, and if complete work up shows no evidence of pancreatitis, study drug/study regimen may be continued or resumed.
 
Note: Study drug/study regimen should be permanently discontinued in Grade 3 events with high likelihood for morbidity and/or mortality – e.g., myocarditis, or other similar events even if they are not currently noted in the guidelines.
 
Similarly, consider whether study drug/study regimen should be permanently discontinued in Grade 2 events with high likelihood for morbidity and/or mortality – e.g., myocarditis, or other similar events even if they are not currently noted in the guidelines – when they do not rapidly improve to Grade <1 upon treatment with systemic steroids and following full taper.
 
Note: There are some exceptions to permanent discontinuation of study drug for Grade 4 events (i.e., hyperthyroidism, hypothyroidism, Type 1 diabetes mellitus).
	
guidelines – when these events are not responding to systemic steroids.
 
 – With long-term steroid and other immunosuppressive use, consider need for Pneumocystis jirovecii pneumonia (PJP, formerly known as Pneumocystis carinii pneumonia) prophylaxis, gastrointestinal protection, and glucose monitoring. – Discontinuation of study drug/study regimen is not mandated for Grade 3/Grade 4 inflammatory reactions attributed to local tumor response (e.g., inflammatory reaction at sites of metastatic disease and lymph nodes). Continuation of study drug/study regimen in this situation should be based upon a benefit/risk analysis for that patient.

Abbreviations: AE = Adverse event; CTC = Common Toxicity Criteria; CTCAE = Common Terminology Criteria for Adverse Events; imAE = immune-mediated adverse event; IV = intravenous; NCI = National Cancer Institute; PO = By mouth.

Specific Immune-Mediated Reactions			
Adverse Events	Severity Grade of the Event (NCI CTCAE version 4.03)	Dose Modifications	Toxicity Management

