Myocarditis	Any Grade	General Guidance Discontinue drug permanently if biopsy-proven immune-mediated myocarditis.	
For Any Grade:
 
 - The prompt diagnosis of immune-mediated myocarditis is important, particularly in patients with baseline cardiopulmonary disease and reduced cardiac function. - Consider, as necessary, discussing with the study physician. - Monitor patients for signs and symptoms of myocarditis (new onset or worsening chest pain, arrhythmia, shortness of breath, peripheral edema). As some symptoms can overlap with lung toxicities, simultaneously evaluate for and rule out pulmonary toxicity as well as other causes (eg, pulmonary embolism, congestive heart failure, malignant pericardial effusion). A Cardiology consultation should be obtained early, with prompt assessment of whether and when to complete a cardiac biopsy, including any other diagnostic procedures. - Initial workup should include clinical evaluation, BNP, cardiac enzymes, ECG, echocardiogram (ECHO), monitoring of oxygenation via pulse oximetry (resting and exertion), and additional laboratory workup as indicated. Spiral CT or cardiac MRI can complement ECHO to assess wall motion abnormalities when needed. - Patients should be thoroughly evaluated to rule out any alternative etiology (eg, disease progression, other medications, or infections)
	Grade 1 (asymptomatic with laboratory (e.g., BNP) or cardiac imaging abnormalities)	No dose modifications required unless clinical suspicion is high, in which case hold study drug/study regimen dose during diagnostic workup for other etiologies. If study drug/study regimen is held, resume after complete resolution to Grade 0.	
For Grade 1 (no definitive findings):
 
 - Monitor and closely follow up in 2 to 4 days for clinical symptoms, BNP, cardiac enzymes, ECG, ECHO, pulse oximetry (resting and exertion), and laboratory workup as clinically indicated. - Consider using steroids if clinical suspicion is high.

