Hepatic function abnormality is defined as any increase in ALT or AST to greater than $3 \times$ ULN and concurrent increase in total bilirubin to be greater than $2 \times$ ULN. Concurrent findings are those that derive from a single blood draw or from separate blood draws taken within 8 days of each other. Follow-up investigations and inquiries will be initiated promptly by the investigational site to determine whether the findings are reproducible and/or whether there is objective evidence that clearly supports causation by a disease (for example, cholelithiasis and bile duct obstruction with distended gallbladder) or an agent other than the investigational product.

Guidelines for management of patients with hepatic function abnormality are outlined in Section [7.2.4](#).

Gastrointestinal disorders

Diarrhea/colitis is the most commonly observed treatment-emergent SAE when tremelimumab is used as monotherapy. In rare cases, colon perforation may occur that requires surgery (colectomy) or can lead to a fatal outcome if not properly managed.

Guidelines on management of diarrhea and colitis in patients receiving study treatment are provided in Section [7.2.4](#).

Endocrine disorders

Immune-mediated endocrinopathies include hypophysitis, adrenal insufficiency, and hyper- and hypothyroidism. Guidelines for the management of patients with immune-mediated endocrine events are provided in Section [7.2.4](#).

Pancreatic disorders

Immune-mediated pancreatitis includes autoimmune pancreatitis, and lipase and amylase elevation. Guidelines for the management of patients with immune-mediated pancreatic disorders are provided in Section [7.2.4](#).

Neurotoxicity

Immune-mediated nervous system events include encephalitis, peripheral motor and sensory neuropathies, Guillain-Barré, and myasthenia gravis. Guidelines for the management of patients with immune-mediated neurotoxic events are provided in Section [7.2.4](#).

Nephritis

Consult with Nephrologist. Monitor for signs and symptoms that may be related to changes in renal function (eg, routine urinalysis, elevated serum blood urea nitrogen [BUN] and creatinine, decreased creatinine clearance, electrolyte imbalance, decrease in urine output, proteinuria, etc).

Patients should be thoroughly evaluated to rule out any alternative etiology (eg, disease progression, infections, etc).

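### Attachment 7 prints the Hy's law permanent stop only under Grade 3, while the Grade 2 hepatitis row covers part of the same laboratory range and allows treatment to resume

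*Protocol*

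**What the plan says.** Protocol Attachment 7 (Specific Immune-Mediated Reactions, Hepatitis) has rows for Any Grade, Grade 1, Grade 2, and Grade 3 or 4.

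- **Grade 3 or 4 row.** After the Grade 3 sub-heading and before the Grade 4 one, it says: "Permanently discontinue study drug/study regimen for any case meeting Hy's law criteria". The criteria given are AST and/or ALT >3x ULN plus bilirubin >2x ULN, with no cholestasis at onset and no alternative cause.
- **Grade 2 row.** This covers AST or ALT >3x to 5x ULN and/or bilirubin >1.5x to 3x ULN. Treatment is held. The Grade 3 or 4 instructions apply only if the event worsens. If values return to Grade 1 or lower "or baseline, resume study drug/study regimen after completion of steroid taper". The row has its own special case for isolated asymptomatic AST elevation, but none for Hy's law.
- **Any Grade row.** This asks for liver test monitoring and a search for other causes. It contains no stop.

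Protocol section 7.2.4.1 governs resumption generally: if appropriate, "in the opinion of the investigator and upon agreement with the sponsor, study treatment may resume upon resolution of clinically significant AEs to baseline" or to below Grade 2.

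**The concern.** A site grades the event and then reads the row for that grade. For a Grade 2 hepatitis event, that row says hold, wait for recovery, finish any taper and resume. The instruction never to redose a Hy's law case sits one row down, under a sub-heading for a different grade. At stake is whether a patient with possible serious drug-induced liver injury may be treated again. Attachment 7 covers both combinations and is not limited to one part of the study or one cycle, so the question can arise in Part A or Part B at any time on treatment.

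**Working it through.** The protocol states no figure to reproduce. The check sets the grade bands against the Hy's law limits and then looks for the stop elsewhere.

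**Inputs (Attachment 7, Hepatitis, multiples of ULN)**

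| Measure | Grade 1 | Grade 2 | Grade 3 | Grade 4 | Hy's law limit |
|---|---|---|---|---|---|
| AST or ALT | >1 to 3 | >3 to 5 | >5 to 20 | >20 | >3 |
| Bilirubin | >1 to 1.5 | >1.5 to 3 | >3 to 10 | >10 | >2 |

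The event grade is taken as the worse of the two measures.

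**Overlap with Grade 2**

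- AST/ALT: above max(3, 3) = 3, up to 5.
- Bilirubin: above max(1.5, 2) = 2, up to 3.

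Stepping through both measures in units of 0.1x ULN gives the same region. The Grade 2 values that meet both limits run from 3.1 to 5.0 for AST/ALT and from 2.1 to 3.0 for bilirubin. The rest of the Hy's law range falls in Grades 3 and 4. None falls in Grade 1, because AST/ALT must exceed 3x.

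**Example.** ALT 4x and bilirubin 2.5x ULN, no cholestasis, no other cause. ALT is Grade 2 (3 < 4 ≤ 5) and bilirubin is Grade 2 (1.5 < 2.5 ≤ 3). Hy's law is met (4 > 3 and 2.5 > 2). The Grade 2 row allows resumption after recovery; the sentence under Grade 3 forbids it.

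**Does another section state the stop for this range?**

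- *Attachment 8, hepatic function abnormalities.* It uses the same >3x and >2x limits and asks for prompt follow-up, but has no stop: "Guidelines for management of patients with hepatic function abnormality are outlined in Section" 7.2.4.
- *Section 7.2.4.1.* It says "there are certain circumstances in which study drugs should be permanently discontinued" and refers back to Attachment 7, which closes the circle.
- *Section 8.1.5.* At ALT ≥5x with bilirubin ≥2x ULN, "clinical and laboratory monitoring should be initiated by the investigator". This is monitoring only, and ALT above 3x but below 5x does not reach it. For patients who enter with ALT ≥3x, the trigger is twice baseline, so at least 2 × 3 = 6x, also above the Grade 2 band.
- *Attachment 7, General Considerations.* Sites should "consider whether study drug/study regimen should be permanently discontinued in Grade 2 events with high likelihood for morbidity and/or mortality" if they do not improve rapidly. That is advice to consider a stop, not an order.
- *Section 6.3.2.* It has a general criterion for unacceptable toxicity but no Hy's law criterion.
- *Attachment 7, Non-Immune-Mediated Reactions, Grade 2.* It says to hold until recovery and has no Hy's law stop.

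**How Attachment 7 places other stops of this kind.** The Any Grade row for myocarditis reads "Discontinue drug permanently if biopsy-proven immune-mediated myocarditis". The stop for bullous rash is also in an Any Grade row. The hepatitis Any Grade row has no counterpart.

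**Frequency.** The documents give no rate for either combination. Section 5.1.2 reports AST rises in 19 of 64 patients on LY3022855 alone (19/64 = 29.7%), with no bilirubin elevation at the time. That cannot settle the rate with a checkpoint inhibitor added; section 5.3 says immune-related events may be more frequent in combination. No expected number of cases is offered here.

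**The case against.** The best reply is that the sentence carries its own scope. It covers any case, and its limits of 3x and 2x lie below the Grade 3 floors of 5x and 3x, so a Grade 3-only reading makes little sense of them. The sub-heading does not strictly confine its contents either. The sentence just before, also under Grade 3, stops treatment above 8x transaminases or 5x bilirubin with no upper bound, so it reaches into Grade 4. Within Grade 3 itself, ALT 6x with bilirubin 2.5x ULN meets both the hold-and-resume bullets and the Hy's law stop. No exception is written there, yet the stop plainly governs. The same reading, specific over general, would settle Grade 2. In addition, section 7.2.4.1 makes resumption permissive and subject to sponsor agreement, and section 6.3.2 lets investigator or sponsor stop for unacceptable toxicity.

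All of this stands as evidence of intent. A reader might infer that the protocol permits, or even directs, redosing of Grade 2-range Hy's law cases; the documents do not support that. What the reply leaves open is findability. The any-grade reading has to be worked out from a row that a site handling a Grade 2 event is sent to only if the event worsens. The sponsor agreement meant to catch an error would be based on the same table.

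**Conclusion.** The conflict is real but narrow. It affects cases with AST/ALT above 3x to 5x ULN and bilirubin above 2x to 3x ULN that also have no initial cholestasis and no alternative cause. Other patients in that laboratory range belong in the Grade 2 row as written, so it would be wrong to infer that everyone there must stop permanently.

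The intended rule is a permanent stop at any grade. Wrongful rechallenge is unlikely, given the required recovery, completed taper and sponsor agreement. The fault is one of placement: a liver-safety stop is missing from the row a site would use, and no other section states it. It should be corrected because the consequence of an error is serious and the correction is simple.

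A reader might also infer that the gap disturbs dose escalation. The documents do not support making that part of the point. Section 7.2.2 requires documented agreement before any escalation, with safety data as the main criterion, so the event would be seen. Other mandatory stops that Attachment 7 applies at Grade 2 are not dose-limiting toxicities by grade alone either.

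The conclusion rests on the grade bands and row layout in the current Attachment 7 and on grading by the worse of the two measures. It does not depend on any assumed event rate.

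**What to change.** In Attachment 7, Hepatitis, move the Hy's law sentence to the Any Grade row or repeat it there, as is done for myocarditis. Alternatively, add to the Grade 2 row: *except cases meeting Hy's law criteria: permanently discontinue*. Either change gives one answer for the whole Hy's law range.

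The cost is one sentence. No new tests, visits or analyses are needed; AST, ALT, bilirubin and alkaline phosphatase are already in the Attachment 2 chemistry panels. The one downside is that patients with Grade 2-range Hy's law cases clearly lose the option to resume after recovery, which the present wording of the stop already implies.
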